3.2 Study Period

The overall study period for each subject is up to 16 weeks. The study periods are as follow:

- Pre-screening period: Day -43 to Day -15, up to 28 days;
- Screening period: Day-14 to Day -2, up to 13 days;
- In-house period: day -1 to Day 3, total 4 days;
- Outpatient period: Day 4 to Day 75, total 72 days;
- End of study visit: Day 75.

3.3 Endpoints and Associated Variables

3.3.1 Pharmacokinetic Variables

Pharmacokinetic concentration data will be obtained at the time points described in schedule of assessment (Table 1).

The following PK parameters will be determined for mavacamten in plasma following single dose administration:

Parameter	WNL Name	CDISC Name	Definition
C _{max}	Cmax	CMAX	Maximum Plasma Drug Concentration
t _{max}	Tmax	TMAX	Time corresponding to occurrence of C_{max}
t1/2	HL_Lambda_z	LAMZHL	Apparent terminal elimination half-life
AUC(0-last)	AUClast	AUCLST	AUC from time zero to the last quantifiable concentration
AUC(0-inf)	AUCINF_obs	AUCIFO	AUC from time zero extrapolated to infinity
%AUC _{ex}	AUC_%Extrap_obs	AUCPEO	Percentage of $AUC_{(0-inf)}$ obtained by extrapolation t_{last}
CL/F	Cl_F_obs	CLFO	Apparent clearance following oral administration
V _z /F	Vz_F_obs	VZFO	Apparent volume of distribution during terminal phase
DNCmax	DNCmax	DNCMAX	Dose normalized Maximum Plasma Drug Concentrati on
DNAUC _(0-last)	DNAUClast	DNAUCLST	Dose normalized AUC from time zero to the last quantifiable concentratio n

Table 3-1 Pharmacokinetic Parameters after Single Dose Administration

Shanghai LianBio Development Co., Ltd. LB2001-101

Parameter	WNL Name	CDISC Name	Definition
DNAUC _(0-inf)	DNAUCINF_obs	DNAUCIFO	Dose normalized AUC from time zero extrapolated to infinity

3.3.2 Safety Variables

Safety will be assessed throughout the study, or at the time points described schedule of assessment (Table 1).

• Adverse events (AEs)

Adverse Event (AE)

An AE is any untoward medical occurrence in a subject after receiving the investigational product and does not necessarily have a clear causal relationship with the investigational drug. An AE can therefore be any unfavorable and unintended sign (e.g., tachycardia, enlarged liver, clinically significant or abnormal laboratory result), subject-reported symptom (e.g., nausea, chest pain), or evidence of any disease activity temporally associated with the use of a study medication, whether or not related to the use of the study medication.

Drug Taken Period Adverse Event

A drug taken period AE will be defined as any AE that emerge during treatment (i.e., AE which started after study drug administration or pre-existed that worsened in severity after study drug administration).

Adverse Events of Special Interest (AESI)

Symptomatic overdose, outcomes of a pregnancy, and LVEF $\leq 30\%$ as determined by local site are considered as Adverse Events of Special Interests (AESIs).

Serious Adverse Event (SAE)

A SAE is an AE that fulfills one or more of the following criteria in the opinion of the investigator or sponsor:

- Results in death;
- is immediately life-threatening (places the subject at immediate risk of death from the event as it occurred);
- Requires subject hospitalization or prolongation of existing hospitalization;
- Resulting in persistent or significant disability or incapability or substantial disruption of the ability to conduct normal life functions.
- Results in a congenital abnormality or birth defect.

Is an important medical event that may not result in death, be life-threatening, or require hospitalization, but may be considered a SAE when, based upon appropriate medical judgment, it may require medical or surgical intervention to prevent one of the outcomes listed above.

• Physical examination findings:

Complete physical examination: general appearance, skin, head and neck, mouth, lymph nodes, thyroid, abdomen, and musculoskeletal, cardiovascular, neurological, and respiratory systems.

Brief physical examination: cardiovascular and respiratory examinations.

- ECG parameters: HR, rhythm, PR interval, QRS interval, QT interval, P wave, QRS complex, T wave morphology, ST segment displacement.
- Vital signs: Systolic blood pressure (SBP) [mmHg], Diastolic blood pressure (DBP) [mmHg] Respiratory rate (bpm), Heart rate (bpm), temperature [°C].
- Clinical laboratory tests:

Hematology	Coagulation	Blood chemistry	Urinalysis ^a
	function		
 White blood cell count including differential Red blood cell count Hemoglobin Haematocrit Platelet count 	function•PT•INR•APTT•TT•FIB	 Sodium Potassium Chloride Calcium Magnesium Urea nitrogen Creatinine Uric acid ALP ALT AST Total bilirubin Direct bilirubin Total protein 	 Specific gravity urine Urine pH Protein urine Urine glucose Urine leukocyte esterase Urine ketone body Red blood cells urine White blood cells urine
		AlbuminCK	
		 Glucose 	

Table 3-2Laboratory Tests

Abbreviations: ALP = alkaline phosphatase; <math>ALT = alanine aminotransferase; APTT = activated partial thromboplastin time; AST = aspartate aminotransferase; CK = creatine kinase; FIB = fibrinogen; FSH = follicle stimulating hormone; HIV = human immunodeficiency virus; INR = international normalized ratio; PT = prothrombin time; SAE = serious AE; TT = thrombin time.

^aUrine microscopy will be performed if there is a significant abnormality in the dipstick.

Safety laboratory assessments (hematology, blood chemistry, coagulation test, urinalysis) has no need to be repeated on Day -1 if latest results are within 7 days.

The following non-safety laboratory parameters will be measured at screening:

- Hepatitis virus test (HBV and HCV): HBV antigen, HCV antibody;
- HIV test: HIV antibody
- FSH (post-menopausal females only);
- Pregnancy test (β-hCG) (all women of childbearing potential);

Shanghai LianBio Development Co., Ltd. LB2001-101

• Alcohol or drug abuse test

3.3.3 Exploratory Variables

Population PK model may be assessed to investigate ethnic differences on key PK parameters

including clearance and volume of distribution.

4 STATISTICAL METHODS

4.1 Data Quality Assurance

All tables, figures and data listings to be included in the report will be independently checked for consistency, integrity and in accordance with standard Parexel procedures.

4.2 General Presentation Considerations

'Baseline' is defined as the last available pre-treatment assessment. 'End of Study' is defined as the last available post-treatment assessment.

Continuous data will be summarized in terms of the mean, standard deviation (SD), upper quartile, median, lower quartile, minimum, maximum and number of observations, unless otherwise stated.

The minimum and maximum will be reported to the same number of decimal places as the raw data recorded in the database. The mean, median, lower quartile and upper quartile will be reported to one more decimal place than the raw data recorded in the database. The SD will be reported to two more decimal places than the raw data recorded in the database. In general, the maximum number of decimal places reported shall be four for any summary statistic.

Categorical data will be summarized in terms of the number of subjects providing data at the relevant time point (n), frequency counts and percentages.

Percentages will be presented to one decimal place. Percentages will not be presented for zero counts. Percentages will be calculated using n as the denominator.

Changes from baseline in categorical data will be summarized using shift tables where appropriate.

P-values greater than or equal to 0.001, in general, will be presented to three decimal places. P-values less than 0.001 will be presented as "<0.001".

Confidence intervals will be presented to one more decimal place than the raw data.

4.3 Software

All report outputs will be produced using SAS[®] version [9.4] or a later version in a secure and validated environment.

PK analyses will be produced using Phoenix[®] WinNonLin (WNL) version [8.2] or a later version in a secure and validated environment.

All report outputs will be provided to the Sponsor in RTF format and can be combined to a whole PDF file.

4.4 Study Subjects

4.4.1 Analysis Sets

Enrolled Analysis Set (ENR): All subjects who have signed informed consent without screening failure.

Pharmacokinetics Set (PKS): The pharmacokinetic (PK) analysis set consists of all subjects exposed to mavacamten with at least one plasma drug concentration result and without serious protocol violations affecting the PK parameter results. The PKS will be used for PK analysis.

Safety Analysis Set (SAS): All subjects exposed to mavacamten, regardless of the doses administered, will be included in the SAS. The SAS is used for safety analysis.

A summary table with the number of subjects in each of the analysis set will be provided and this table will be displayed by cohort and overall, for ENR. A listing of subjects excluded from analysis sets will also be provided including reason of exclusion for ENR.

A by-subject listing of analysis set details will be provided. This listing will be presented by cohort and include subject identifier, inclusion/exclusion flag and reason for exclusion from each analysis set. All subjects screened will appear on this listing.

4.4.2 Disposition of Subjects

Screening failures (i.e., subjects who signed the ICF but do not receive study treatment) and the associated reasons for failure will be tabulated overall.

A summary of study treatment status will be provided for the ENR. This display will show the number and percentage of subjects who have completed the study or have discontinued study treatment and a summary of the primary reasons for discontinuation of study treatment.

A -by subject listing of study treatment discontinuation will be presented for the ENR. The listing will include reasons for discontinuation of study treatment.

4.4.3 **Protocol Deviations**

All protocol deviations are predefined in the separate document, Protocol Deviation Specification.

4.4.3.1 Protocol Deviations with Non-PK Implications

The defined protocol deviations will be collected during the study period by site monitor/clinical team and programming team. All deviations related to study inclusion or exclusion criteria, conduct of the study, subject management or subject assessment, and handling of the subject's rights will be described.

4.4.3.2 Protocol Deviations with PK Implications

Protocol deviations that may potentially impact PK parameter derivation include, but are not limited to:

- Emetic episode in case of orally administered study drug
- Missed PK samples that impact estimation of PK parameter(s)
- Concomitant medications not authorized by protocol

• PK samples obtained out of allowance window that may impact the estimation of PK parameter(s)

Protocol deviations (mentioned in Sections 4.4.3.1 and 4.4.3.2) and analysis sets will be reviewed in the data review meeting (DRM) to decide analyses sets and to decide if special subject's data will be excluded from certain analyses. Decisions regarding the exclusion of subjects and/or data from analyses will be made prior to database lock and will be documented and approved.

A -by subject listing of major and minor protocol deviations will be provided including subject identifier; leading to exclusion from specific analysis sets; and protocol deviation classification, and protocol deviation description.

4.5 Demographics and Baseline Characteristics

The demographic characteristics (age, gender, ethnic, height, body weight, body mass index [BMI]), CYP2C19 genotypes will be summarized by cohort and overall and listed by subject for the SAS.

4.6 Medical History and Concomitant Illnesses

All medical history and concomitant illnesses will be coded to System Organ Class (SOC) and Preferred Term (PT) using the MedDRA version 24.0 or later version. All medical history and concomitant illnesses will be summarized by SOC and PT by cohort and overall for the SAS.

A by-subject listing of medical history and concomitant illnesses will be also provided.

4.7 **Prior and Concomitant Medications**

Medications will be considered as prior if they with a stop date prior to administration of the study drug.

Medications will be considered as concomitant if they are stopped on or after administration of the study drug.

All concomitant medications will be coded to Anatomical Therapeutic Chemical (ATC) classification and PT using the World Health Organization Drug Dictionary (WHO-DD) SEP 2020 or later version. All concomitant medications will be summarized by ATC and PT for the SAS.

A by-subject listing will be provided with relevant information for prior and concomitant medications.

4.8 Pharmacokinetics

4.8.1 Pharmacokinetic Concentrations

Concentration Listings:

Pharmacokinetic concentration data for mavacamten, will be listed by cohort and subject for the PKS. Concentration listings will include nominal PK sampling time, actual sampling times relative to dose administration, deviation from nominal time, and percent deviation from nominal time, and concentrations. Plasma concentrations below the lower limit of quantification (LLOQ) will be presented as below the lower limit of quantification (BLQ) in the listings. Missing PK samples will be reported as no sample (NS) and/or not reportable (NR) and considered to be excluded from PK analysis.

In concentration listings, the individual concentrations will be reported to the same precision as the source data (for example, if the source data is presented to five significant digits in Bioanalytical

Lab deliverable, it will be programmed to same precision in SDTM and ADaM PK concentration datasets, and the individual values in the listings will be presented to five significant digits).

Concentration Summary Tables:

Tabular summaries for concentration-time data will report N (number of subjects who received treatment) and n (number of subjects with non-missing values).

Concentration for mavacamten will be summarized by cohort, and nominal timepoint for the PKS. The following descriptive statistics will be presented for plasma concentrations obtained at each nominal time point: N, n, arithmetic mean, SD, coefficient of variation (CV%), geometric mean, geometric CV% (calculated as: $gCV\% = SQRT(e^{s^2}-1)*100$; where s is the SD of the log-transformed values), median, minimum, and maximum values.

The rules followed for calculation and presentation of concentration data with regards to the number of decimal places/significant digits for the listings of subject level concentrations and summary tables of concentration are as follows:

- Source data will be used for calculation of concentration summary statistics.
- For presentation in concentration summary tables if less than 4 significant digits, all summary statistics will be tabulated to one more significant digit compared to the source data, otherwise up to a maximum of four significant digits, except that N and n will be presented as whole numbers.
- CV% and gCV% will be presented in one decimal place.

Concentration Figures:

To visualize subject-level concentrations and the comparison between each cohort, the descriptive PK graphs listed below will be generated.

- Figure 1: Individual overlaid profiles for mavacamten (0-24h): Plasma Concentration Time Data (Linear Scale and Semi-Logarithmic Scale) (PKS)
- Figure 2: Overlaid individual subject profiles for mavacamten: Plasma Concentration Time Data (Linear Scale and Semi-Logarithmic Scale) (PKS)
- Figure 3: Mean (± SD) mavacamten overlaid profiles per cohort (0-24h): Plasma Concentration Time Data (Linear Scale and Semi-Logarithmic Scale) (PKS)
- Figure 4: mavacamten Mean (± SD) overlaid profiles per cohort: Plasma Concentration Time Data (Linear Scale and Semi-Logarithmic Scale) (PKS)

Figures will be generated in color using unique line style and marker for each plot in the graph. For all PK concentration-time plots, linear scale will be used for x-axis (e.g., do not use an ordinal scale).

4.8.2 Handling of Concentration Values Below the Limit of Quantification (BLQ)

Derivation of plasma PK parameters

- BLQs at the beginning of a subject profile (i.e., before the first incidence of a measurable concentration) will be assigned to zero.
- BLQs at the end of a subject profile (i.e., after the last incidence of a measurable concentration) will be set to missing.
- Single BLQs which fall between two measurable concentrations will be set to missing.

• Consecutive BLQs (2 or more) which fall between measurable concentrations will be set to missing. Measurable concentrations after consecutive BLQs will also be set to missing.

Concentration Listings:

All BLQ concentrations will be labeled as "BLQ" in the concentration data listings, and LLOQ value presented as a footnote.

Concentration Figures:

For arithmetic mean linear/linear graphs, all BLQ values will be substituted with zero for calculation of arithmetic mean and for log/linear graphs the log transformed arithmetic mean will be displayed (this should not include zero).

For individual linear/linear and log/linear graphs all BLQ values will be substituted as follows:

- BLQs at the beginning of a subject profile (i.e., before the first incidence of a measurable concentration) will be assigned to zero (except for intravenous administration when these BLQs should not be displayed). When using log/linear scale, these timepoints will be considered missing.
- BLQs at the end of a subject profile (i.e., after the last incidence of a measurable concentration) will be set to missing.
- Single BLQs which fall between two measurable concentrations will be set to missing.
- Consecutive BLQs which fall between measurable concentrations will be set to missing. Measurable concentrations after consecutive BLQs will be set to missing.

Concentration Tables:

For summary tables, all BLQs will be considered zero, and number of BLQs and non-BLQs at each scheduled time point will be reported. Summary Statistics will not be calculated if non-BLQ concentrations at a scheduled time point is <3 and reported as NC.

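### The SAP sets BLQ values to zero in the concentration tables without exempting the geometric mean and gCV%, so in mixed rows the first becomes zero and the second cannot be computed (minor)

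*SAP*

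**What the plan says.** SAP 4.8.1 (Concentration Summary Tables) lists the statistics to be shown for each cohort at each nominal time, among them "arithmetic mean, SD, coefficient of variation (CV%), geometric mean, geometric CV"%. It defines gCV% as the square root of exp(s²) − 1, times 100, "where s is the SD of the log-transformed values". It also fixes the counts to be printed: "Tabular summaries for concentration-time data will report N (number of subjects who received treatment) and n (number of subjects with non-missing values").

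SAP 4.8.2 (Concentration Tables) then gives the BLQ rule for the same tables: "For summary tables, all BLQs will be considered zero, and number of BLQs and non-BLQs at each scheduled time point will be reported". Its only suppression rule is: "Summary Statistics will not be calculated if non-BLQ concentrations at a scheduled time point is <3 and reported as NC".

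The same section treats the log scale separately for figures. For mean log/linear graphs it says of the plotted mean that "this should not include zero". For BLQs at the start of an individual profile it says: "When using log/linear scale, these timepoints will be considered missing". The paragraph on tables has no counterpart. The protocol gives no BLQ rule of its own.

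**The concern.** Zero has no logarithm, and both the GM and the gCV% are built on logarithms. A row with three or more quantifiable values and one or more BLQs passes the suppression rule and goes forward with zeros in it. The two adjacent sections then ask for statistics that the substituted data cannot usefully supply.

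The stake is reproducibility of a descriptive table. A programmer who follows the text literally prints a GM of zero and hits an error or a blank for gCV%. One whose software discards ln(0) prints a GM and gCV% for the quantifiable subjects only, beside an n and an arithmetic mean that include the zeros. PK is the primary objective, and two people following this SAP could print different numbers in the same cell.

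**Working it through.** **1. Apply the rule to a row.** With GM = exp(mean of ln x) and gCV% = 100 × √(exp(s²) − 1), take an invented row of 12: eight quantifiable values (1.2, 1.5, 1.8, 2.1, 2.6, 3.0, 3.5, 4.1 ng/mL) and four BLQs. Eight values are non-BLQ, so the row is not suppressed.

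| Handling of the four BLQs | GM | gCV% |
|---|---|---|
| Zero, as written | 0 | not computable |
| Left out of the log statistics (n = 8) | 2.29 | 44.6 |
| Half of an assumed LLOQ of 1 ng/mL (n = 12) | 1.38 | 98.4 |

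The arithmetic mean with zeros is 19.8/12 = 1.65. It, the SD, median, minimum and maximum can all be computed. Only the two log-based cells fail, and their values depend heavily on the convention chosen.

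**2. What happens if software drops ln(0).** The SAP does not say that it will. Take 9 BLQs and 3 values of 1.5 ng/mL. A zero is not missing, so n = 12. The arithmetic mean is (3 × 1.5)/12 = 0.375 and the GM is 1.5. The row must also report 9 BLQ and 3 non-BLQ values. The GM's n would be that 3, but nothing in the SAP ties the two together.

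**3. Will mixed rows occur?** A mixed row here has 3 to n − 1 values at or above the LLOQ. The inputs come from protocol Table 3:

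- UM/RM/NM (Japanese, 25 mg): half-life 153.8 h (CV 50.5%), V/F 306.8 L (30.8%), CL/F CV 30.6%.
- IM, 15 mg: half-life 221.5 h (23.0%), V/F 310.9 L (26.0%), CL/F CV 29.2%.
- PM, 15 mg: half-life 571.6 h (24.5%), V/F 282.3 L (14.9%), CL/F CV 22.1%.

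The model is C(t) = (dose/V) × exp(−ln 2 × t / half-life) at nominal times, with cohorts of 12, 12, 12 and 8. For a typical Cohort 2 subject on Day 45 (1056 h): 25,000,000 ng / 306,800 mL = 81.5 ng/mL, times exp(−0.693 × 1056/153.8) = 0.0086, which gives 0.70 ng/mL. By Day 60 (1416 h) it is 0.14 ng/mL.

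Half-life and V/F were drawn as lognormal. Their log-scale correlation was set so that the implied CL/F CV matches Table 3: 0.795 for UM/RM/NM, 0.303 for IM and 0.455 for PM. As a check, the implied mean CL/F is 1548, 1007 and 357 mL/h, against 1505, 1006 and 357.1 in Table 3. Expected mixed rows among the 7 from Day 14 to Day 75, from 100,000 simulated cohorts each:

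| Assumed LLOQ (ng/mL) | 0.1 | 0.5 | 1 | 2 | 5 |
|---|---|---|---|---|---|
| Cohort 1 (UM/RM/NM, 15 mg) | 4.0 | 3.7 | 3.5 | 3.1 | 2.2 |
| Cohort 2 (UM/RM/NM, 25 mg) | 4.0 | 3.9 | 3.7 | 3.4 | 2.8 |
| Cohort 3 (IM, 15 mg) | 1.6 | 2.0 | 1.9 | 2.1 | 2.0 |
| Cohort 4 (PM, 15 mg) | 0 | 0 | 0.04 | 0.3 | 1.5 |

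Before Day 14 the answer also depends on the LLOQ. The Cohort 1 Day 10 row is mixed with probability at most 0.05 for LLOQ up to 2 ng/mL, but 0.27 at 5 ng/mL. Samples from 10 min to 12 h were not modelled, because the documents give no absorption lag.

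**4. What uses these cells.** PK parameters follow a separate BLQ rule in SAP 4.8.2, under which trailing BLQs are set to missing. The ANOVA in SAP 4.8.4 uses AUC and Cmax. The mean figures plot the arithmetic mean and SD. None of them takes the table GM or gCV% as input.

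**The case against.** The strongest case is that the SAP already limits the damage. It requires the BLQ and non-BLQ counts at each time point, so a reader can see that a row is mixed. If ln(0) is dropped, the non-BLQ count is exactly the n behind the GM. Individual values are listed with BLQ labels "in the concentration data listings, and LLOQ value presented as a footnote", so either version can be recomputed. An all-BLQ row, such as a pre-dose row, is caught by the suppression rule. All of this stands, and it is why the point is minor. It does not supply the missing rule: the counts do not say which values entered the GM.

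A reader might infer more than the documents support:

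- **That both statistics are undefined.** By the product definition, the GM of a set containing zero is 0, which is defined but uninformative. Only gCV% cannot be computed.
- **That the tables will mislead without anyone noticing.** That needs software to discard ln(0) silently. The SAP does not state this, and a literal calculation would fail visibly during programming.
- **That the number of affected rows is known.** It depends on an LLOQ that the documents do not give, and the counts move across the assumed range.
- **That the primary PK results are at risk.** They rest on other rules and do not change.

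**Conclusion.** The rule is wrong as written, and the consequence is minor. Applied literally, SAP 4.8.1 and 4.8.2 together give a GM of zero and no gCV% in every row with at least 3 quantifiable values and at least one BLQ. That follows from the text alone and needs no assumption.

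How often it happens is less certain. For LLOQ values of 0.1 to 5 ng/mL, expect about 2 to 4 of the 7 late rows in each UM/RM/NM cohort, about 2 in the IM cohort and 0 to 1.5 in the PM cohort. These counts assume mono-exponential decline, lognormal variation, no assay error, nominal sampling times, full attendance and Table 3 values from groups of 8, with the same half-life and volume at 15 and 25 mg for UM/RM/NM. They show that mixed late rows are likely and do not predict an exact number.

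**What to change.** Add one sentence to SAP 4.8.2, Concentration Tables: *Zero substitution does not apply to the geometric mean and gCV%; these will be calculated from non-BLQ values only, and the reported non-BLQ count is their n.* The alternative is to report both as NC in any row with a BLQ. Either works, but the SAP should state one. Keep the other statistics, the BLQ counts and the fewer-than-3 rule as they are.

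The cost is that sentence and a footnote in the table shell. Under the first option the two cells describe quantifiable subjects only, and the GM can exceed the arithmetic mean in the same row. Under the alternative, rows with only one or two BLQs lose their GM and gCV%.
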